6.1.4 ATI

For all participants, initiation of ATI is defined as Day 0.

While on Schedule 1, participants will undergo the following procedures, as specified in [Appendix E](#) and [Appendix H](#):

- Complete physical examination OR Targeted (ie, symptom directed) physical examination, including weight and vital signs
- Assessment of concomitant medications
- Intercurrent illness/adverse experiences (AEs)
- ART re-initiation assessment
- HIV transmission risk behavior assessment and counseling
- Contraception status assessment (for participants who are capable of becoming pregnant and who are sexually active in a way that could lead to pregnancy; see Section [6.6](#) and [Appendix B](#))

- Decision-making assessment
- Psychosocial assessment
- Social impact assessment
- Social impact assessment questionnaire
- Blood collection per [Appendix E](#) for:
 - HIV PCR viral load
 - CD4+ and CD8+ T-cell counts
 - Hgb, ANC, platelets
 - ALT, direct bilirubin, eGFR
 - Syphilis testing
 - ARV detection
 - Intracellular cytokine staining (ICS)
 - Immune cell phenotyping
 - Neutralizing antibodies (nAb)
 - Fragment crystallizable receptor (FcR)-mediated effector functions
 - HIV reservoir assessment
 - Blood hormone levels (estradiol and progesterone)
 - Serum, plasma, and PBMC storage
- Urine pregnancy test (persons not of reproductive potential due to having reached menopause (no menses for 1 year), or having undergone hysterectomy or bilateral oophorectomy or tubal ligation [verified by medical records], are not required to undergo pregnancy testing)
- Gonorrhea/chlamydia testing by urine or cervical/vaginal swab
- Trichomonas testing by cervical/vaginal swab

6.2 Schedule 2: Monitoring ATI with viremia

As soon as participants demonstrate viral load ≥ 200 copies/mL, they will transition to Schedule 2, during which they will continue ATI while viremia is monitored. At Schedule 2 timepoints specified in [Appendix F](#) and [Appendix I](#), participants will undergo the following procedures:

- Complete physical examination OR targeted (ie, symptom directed) physical examination, including weight and vital signs
- Assessment of concomitant medications
- Intercurrent illness/adverse experiences (AEs)
- ART re-initiation assessment
- HIV transmission risk behavior assessment and counseling
- Contraception status assessment (for participants who are capable of becoming pregnant and who are sexually active in a way that could lead to pregnancy; see Section 6.6 and [Appendix B](#)).
- Decision-making assessment
- Psychosocial assessment
- Social impact assessment
- Social impact assessment questionnaire
- Blood collection for:
 - HIV PCR viral load
 - CD4+ and CD8+ T-cell counts
 - Hgb, ANC, platelets
 - ALT, direct bilirubin, eGFR
 - Syphilis testing
 - ARV detection
 - ICS
 - Immune cell phenotyping

- Neutralizing antibodies (nAb)
- FcR-mediated effector functions
- Blood hormone levels (estradiol and progesterone)
- Serum, plasma, and PBMC storage
- Urine pregnancy test (persons not of reproductive potential due to having reached menopause [no menses for 1 year] or having undergone hysterectomy or bilateral oophorectomy [verified by medical records], are not required to undergo pregnancy testing).
- Gonorrhea/chlamydia testing by urine or cervical/vaginal swab
- Trichomonas testing by cervical/vaginal swab

6.3 Schedule 3: Follow-up on ART

After ART re-initiation criteria are met (see Sections [3.3.2](#) and [3.3.3](#)), participants will transition to Schedule 3 once ART is re-initiated (see [Appendix G](#) and [Appendix J](#)). In Schedule 3, if virologic resuppression has not been achieved by Week 12, participants may continue with biweekly visits until viral resuppression is achieved. These additional visits will be treated as interim visits (see HVTN 805/HPTN 093 SSP).

At Schedule 3 timepoints specified in [Appendix G](#) and [Appendix J](#), participants will undergo the following procedures:

- Complete physical examination OR targeted (ie, symptom directed) physical examination, including weight and vital signs
- Assessment of concomitant medications
- Intercurrent illness/adverse experiences (AEs)
- HIV transmission risk behavior assessment and counseling
- Contraception status assessment (for participants who are capable of becoming pregnant and who are sexually active in a way that could lead to pregnancy; see Section [6.6](#) and [Appendix B](#)).
- Decision-making assessment
- Psychosocial assessment

- Social impact assessment
- Social impact assessment questionnaire
- Blood collection for:
 - HIV PCR viral load
 - CD4+ and CD8+ T-cell counts
 - Hgb, ANC, platelets
 - ALT, direct bilirubin, eGFR
 - Syphilis testing
 - HIV genotypic antiretroviral resistance
 - Viral isolation and sequencing
 - ICS
 - Immune cell phenotyping
 - Neutralizing antibodies (nAb)
 - FcR-mediated effector functions
 - HIV reservoir assessment
 - Serum, plasma, and PBMC storage
- Urine pregnancy test (persons not of reproductive potential due to having reached menopause [no menses for 1 year] or having undergone hysterectomy or bilateral oophorectomy [verified by medical records], are not required to undergo pregnancy testing).
- Gonorrhea/chlamydia testing by urine or cervical/vaginal swab
- Trichomonas testing by cervical/vaginal swab

6.4 Interim visits

Confirmatory VL samples and confirmatory CD4+ T cell samples may be drawn at interim visits (see Sections 3.3.1, 3.3.2, and 3.3.3). At interim visits for this purpose, the following clinical procedures will be performed:

- Targeted physical exam
- Assessment of concomitant medications
- Intercurrent illness/adverse experiences (AEs)
- ART re-initiation assessment
- HIV transmission risk behavior assessment and counseling
- Social impact assessment

Additional procedures may be performed at the discretion of the clinician.

For additional information on interim visits, including interim visits for other reasons, see the HVTN 805/HPTN 093 SSP.

6.5 Early termination visit

At an early termination visit for a participant on Schedule 1 or 2, CRS staff should consider performing procedures specified for Extended Visit Type A (see [Appendix E](#), [Appendix F](#), [Appendix H](#), and [Appendix I](#)). Such participants will be urged to re-initiate ART under the care of their primary HIV care provider (see HVTN 805/HPTN 093 SSP for additional details).

At an early termination visit for a participant on Schedule 3, CRS staff should consider performing laboratory procedures specified for Week 40 (Visit 91) and clinic procedures specified for Week 52 (Visit 92) (see [Appendix G](#) and [Appendix J](#); see HVTN 805/HPTN 093 SSP for additional details).

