3.2.3 Exploratory objectives

Exploratory objective 1

- To assess participant and potential participant motivations, perceptions and tolerance for ATIs, for prolonged viremia, and for trial requirements (eg, ART switches, barrier protection for all sexual activity)

Exploratory objective 2

- To assess social benefits (eg, altruism) and negative social impacts, including but not limited to anxiety regarding being off ART and becoming viremic again and fear of inadvertent HIV transmission to partners

Exploratory objective 3

- To assess participant and potential participant decision-making quality, including perception of being informed, clarity and support in decision making and satisfaction with their choice regarding participation

Exploratory objective 4

- To evaluate the effect of VRC01 received in the immediate pre-HIV acquisition period and/or during early infection on viral kinetics in participants undergoing ATI

Exploratory objective 5

- To determine whether characteristics of the transmitted/founder (T/F) viruses, rebound virus(es), and/or baseline viral reservoirs, including relative VRC01 sensitivity or resistance, are associated with virologic control or the development of anti-HIV immunity among individuals who acquired HIV during their participation in HVTN 703/HPTN 081

Exploratory objective 6

- To assess whether host genetics (eg, HLA type, CCR5 heterozygosity) and sex assigned at birth are associated with time to meeting ART re-initiation criteria among VRC01 or placebo recipients who acquired HIV during their participation in HVTN 703/HPTN 081

Exploratory objective 7

- To qualitatively characterize the immune responses and reservoir characteristics of controllers and non-controllers in this cohort and to compare these to immune responses and reservoir characteristics of historical cohorts (ie, SPARTAC African and non-African cohorts, described in Gossez et al (1), comprising individuals who initiated ART early in HIV infection without other interventions)

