⁶ If QuantiFERON TB testing cannot be performed, a tuberculin skin test (TST) should be conducted. Additional risk/clinical/diagnostic assessment may be performed at the discretion of the clinician to meet institutional standard of care for evaluation and treatment of latent TB.

⁷ For specimen collection requirements, see Appendix E.

⁸ Extended follow-up visit type A will occur every 6 months starting with 3 months after visit 27, continuing up to 3 years of this schedule. This follow-up visit may be performed for participants who have not met ART re-initiation criteria (see Protocol Section 3.3 and HVTN 805/HPTN 093 SSP for details).

⁹ Extended follow-up visit type B will occur every 6 months starting with 6 months after visit 27, continuing up 3 years of this schedule and then every 3 months thereafter. This follow-up visit may be performed for participants who have not met ART re-initiation criteria (see Protocol Section 3.3 and HVTN 805/HPTN 093 SSP for details).

¹⁰ At an early termination visit for a withdrawn or terminated participant, CRS staff should consider performing procedures specified for Extended follow-up visit Type A (see Section 6.5 and HVTN 805/HPTN 093 SSP for details).

Procedures at CRS—Schedule 1: Monitoring ATI (continued)

	Visit: Days on ATI:	20 D168	21 D196	22 D224	23 D252	24 D280	25 D308	26 D336	27 D364	Visit Type A ^{8, 10}	Visit Type B ⁹
	Weeks on ATI:	W24	W28	W32	W36	W40	W44	W48	W52		
Study procedures											
Screening consent (if used)											
Protocol consent											
Assessment of understanding											
Medical history											
Complete physical exam											
Targeted physical exam ⁴		✓	✓	✓	✓	✓	✓	✓	✓	✓	✓
Concomitant medications ⁴		✓	✓	✓	✓	✓	✓	✓	✓	✓	✓
Intercurrent illness/adverse experience ⁴		✓	✓	✓	✓	✓	✓	✓	✓	✓	✓
ART re-initiation assessment ⁴		✓	✓	✓	✓	✓	✓	✓	✓	✓	✓
Transmission risk reduction counseling ⁴		✓	✓	✓	✓	✓	✓	✓	✓	✓	✓
Contraception status assessment ⁵		✓	✓	✓	✓	✓	✓	✓	✓	✓	✓
Decision aid											
Decision-making assessment		✓			✓				✓		✓
Psychosocial assessment		✓			✓				✓		✓
Social impact assessment ⁴		✓	✓	✓	✓	✓	✓	✓	✓	✓	✓
Social impact assessment questionnaire		✓			✓				✓		✓
QuantiFERON tuberculosis test ⁶											
Confirm eligibility											
Specimen collection⁷		✓	✓	✓	✓	✓	✓	✓	✓	✓	✓

¹ Screening may occur over the course of several contacts/visits up to and including the day of enrollment as defined in Section 6.1.2.

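### The suggested exit visit for participants leaving the study from Schedule 1 or 2 omits three participant-experience instruments that the Schedule 3 exit visit includes

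*Protocol*

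**What the plan says.** Protocol Section 6.5 gives two exit rules. For Schedules 1 and 2 it says "CRS staff should consider performing procedures specified for Extended Visit Type A". The clinic-procedure tables repeat this in Appendix H footnote 10 and Appendix I footnote 6, where staff "should consider performing procedures specified for Extended follow-up visit Type A". For Schedule 3 the section splits the visit. Laboratory procedures come from Visit 91, while the clinic side is "clinic procedures specified for Week 52 (Visit 92", that is, Visit 92.

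Three instruments in those tables concern how participants experience the study: the decision-making assessment, the psychosocial assessment and the social impact assessment questionnaire. A separate social impact assessment is ticked at every visit from day 0.

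Section 3.2.3 sets the objectives that these instruments bear on. Objective 1 is "To assess participant and potential participant motivations, perceptions and tolerance for ATIs, for prolonged viremia, and for trial requirements". Objective 2 includes "anxiety regarding being off ART and becoming viremic again and fear of inadvertent HIV transmission to partners". Objective 3 concerns decision quality, including satisfaction with the choice about taking part.

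**The concern.** The two exit rules treat these instruments differently. Someone who leaves after restarting ART is offered all three. Someone who leaves during the interruption, with or without viremia, is offered none. Yet the experiences named in objectives 1 and 2 arise mainly while off ART. If some people leave because of those experiences, an exit record from them would be among the more informative data for these objectives. The Schedule 3 rule shows that laboratory and clinic procedures can be drawn from different visits at exit, so the omission for Schedules 1 and 2 is easily avoided.

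**Working it through.** **Step 1. Which visits carry which instrument.** Read from Appendix H (Schedule 1), Appendix I (Schedule 2) and Appendix J (Schedule 3):

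| Visit | Decision-making | Psychosocial | Questionnaire | Social impact assessment |
|---|---|---|---|---|
| Schedule 1, day 0 (Visit 4) | yes | yes | no | yes |
| Schedule 1, one round at about weeks 12–16* | yes | yes | yes | yes |
| Schedule 1, Visits 20, 23, 27 (weeks 24, 36, 52) | yes | yes | yes | yes |
| **Schedule 1, Type A (exit)** | **no** | **no** | **no** | yes |
| Schedule 1, Type B | yes | yes | yes | yes |
| Schedule 2, Visit 40 (entry) | yes | yes | no | yes |
| Schedule 2, Visit 50 (week 12) | no | yes | yes | yes |
| Schedule 2, Visits 56, 62, 66 (weeks 24, 36, 52) | yes | yes | yes | yes |
| **Schedule 2, Type A (exit)** | **no** | **no** | **no** | yes |
| Schedule 2, Type B | yes | yes | yes | yes |
| Schedule 3, Visit 80 (ART re-initiation) | yes | yes | no | yes |
| Schedule 3, Visits 86, 89 (weeks 12, 24) | yes | yes | yes | yes |
| Schedule 3, Visit 91 (exit, laboratory only) | no | no | no | yes |
| **Schedule 3, Visit 92 (exit, clinic)** | **yes** | **yes** | **yes** | yes |

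*Column alignment in the extracted table is uncertain here.

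The exit set therefore has 0 of 3 instruments for Schedules 1 and 2, and 3 of 3 for Schedule 3.

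**Step 2. What earlier rounds leave uncovered.** The questionnaire is not scheduled at day 0 or at Visit 40. A person who leaves Schedule 1 before its first on-interruption round has never completed it. A person who moves to Schedule 2 before that round is next due it at Schedule 2 week 12. On Schedule 2 the decision-making assessment is taken at Visit 40 and not again until week 24.

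**Step 3. How many people.** The documents give no rate for leaving the study while off ART. The nearest figure is in Protocol Section 4.1.1, which assumes censoring at 20% per year from study termination or ART restart before criteria are met. The same section gives the Weibull model (λ = exp(−2.932), p = 2.014), and the planned size is 16 to 61.

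- Check of the plan's median: (ln 2)^(1/2.014) / exp(−2.932) = 15.64 weeks, which agrees with the stated 15.6.
- Censoring by that time: 1 − 0.8^(15.6/52) = 6.5%. This is 0.065 × 16 = 1.0 person and 0.065 × 61 = 4.0 people.
- Censored before meeting criteria, over 72 weeks: integrate c·exp(−ct)·exp[−HR·(λt)^p] from 0 to 72, with c = −ln(0.8)/52 or 0.2/52 as two readings of 20% per year.

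| Hazard ratio applied to all | Censored before criteria | Of 16 | Of 61 | Of which before week 12 |
|---|---|---|---|---|
| 1 (placebo hazard) | 6.1–6.8% | 1.0–1.1 | 3.7–4.2 | 4.0–4.4% |
| 0.4 | 9.5–10.5% | 1.5–1.7 | 5.8–6.4 | 4.3–4.8% |

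At the placebo hazard about two thirds of the censoring falls before week 12 (4.4/6.8 = 0.65).

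**The case against.** The strongest reply is that the protocol already has a route for people who find the interruption hard. On either schedule a participant may ask to restart ART (Sections 3.3.2 and 3.3.3). That leads to Schedule 3, where Visit 80 takes the decision-making and psychosocial assessments. The gap therefore concerns only people who leave the study altogether while off ART. Section 5.3 lists several reasons for leaving that have nothing to do with tolerance, such as relocation. Type A keeps the social impact assessment, and reasons for stopping the interruption and for early termination are tabulated (Section 4.2.5.3). The exit wording is only advisory, and the study-specific procedures document, which is not available here, may add detail. All of this stands and limits the point, but none of it explains why the two exit rules differ.

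A reader might draw three stronger conclusions that the documents do not support:

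- **That the objectives lose the participants who tolerated the interruption worst.** What is lost is an exit measurement. Earlier records remain, and nothing in the documents shows that leavers are the least tolerant.
- **That the last record for leavers dates from day 0.** This can be true of two instruments for someone leaving Schedule 1 before its first on-interruption round. It is not true on Schedule 2, because Visit 40 repeats those two, and the questionnaire has no day 0 record at all.
- **That the summaries will be biased towards good tolerance.** Neither document specifies a summary for exploratory objectives 1 to 3, and the SAP's objectives section does not list them. That direction is plausible but not demonstrated.

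**Conclusion.** The point holds as a small inconsistency in the exit procedures. Participants who leave the study from Schedule 1 or 2 while off ART have no planned exit record on three instruments that Schedule 3 leavers are offered. This weakens exploratory objectives 1 to 3 and touches no primary or secondary endpoint.

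The number affected is at most about 1 of 16 to 4 of 61 by week 15.6. Over the full 72 weeks the placebo-hazard figure is much the same, and it reaches about 6 of 61 only if a hazard ratio of 0.4 applied to everyone. These are ceilings for exits before criteria are met: the 20% per year includes ART restarts, the split is not given, and those who restart within the study are not affected. The count leaves out anyone who meets criteria, declines ART (Section 3.3.4) and then leaves, for whom the documents give no rate. It is a worthwhile, low-priority improvement.

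**What to change.** In Section 6.5, Appendix H footnote 10 and Appendix I footnote 6, keep the Type A laboratory procedures for early termination from Schedule 1 or 2, but name the Type B clinic procedures. The Appendix I note also appears, numbered 10, under the first part of that table, and should be changed there too. This mirrors the Visit 91 and Visit 92 split already used for Schedule 3. The laboratory footnotes (Appendix E footnote 17, Appendix F footnote 13) can stay as they are, which preserves the 59.5 mL PBMC storage draw that Type A has and Type B lacks.

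The change uses existing instruments and adds no visit and no blood. It costs some extra minutes at the exit visit. Some withdrawing participants will decline, and those lost to follow-up may have no exit visit, so the gap will shrink but not close.

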6.6 Contraception status

Contraception status is assessed and documented at every scheduled clinic visit from screening through confirmation of viral resuppression following ART re-initiation for a participant who is capable of becoming pregnant and who is sexually active in a way that could cause that participant to become pregnant. Prior to enrollment and until viral resuppression is confirmed following ART re-initiation, staff will ask participants to verbally confirm their use of adequate contraceptive methods (see [Appendix B](#)). A participant who is sexually active in a way that could cause that participant to become pregnant should be reminded at all scheduled clinic visits of the importance of using effective contraception (ie, IUD or hormonal) in addition to barrier protection (ie, condoms) to prevent HIV transmission to sexual partner(s) and should be referred to specific counseling, information, and advice as needed. This reminder should be documented in the participant's study record.

Infertility—including having reached menopause (no menses for 1 year) or having undergone hysterectomy, bilateral oophorectomy, or tubal ligation—must be documented in the participant’s study record.

6.7 Specific clinical management considerations

6.7.1 Pregnancy or breastfeeding

Volunteers who are pregnant or breastfeeding are not eligible to participate in this study. Participants who become pregnant or are breastfeeding during the ART switch will not be allowed to interrupt ART and will be terminated from the study immediately. Participants who become pregnant or are breastfeeding during the ATI phase will re-initiate ART as soon as possible. Post-ATI follow-up will continue per Schedule 3 for up to 24 weeks after viral re-suppression is confirmed following ART re-initiation.

Participants who become pregnant or begin breastfeeding while on Schedule 3 (ie, after ART re-initiation) will continue per Schedule 3 for up to 24 weeks after viral re-suppression is confirmed.

If a participant completes the study or chooses to discontinue from the study before the pregnancy ends, then CRS staff should request permission to contact the participant regarding pregnancy outcomes at the end of the pregnancy. If obtained, pregnancy outcomes will be recorded on a CRF at the end of the pregnancy. All pregnancies must be reported to the Antiretroviral Pregnancy Registry.

6.7.2 Acute retroviral syndrome (ARS)

ARS is a rare diagnosis to be made by a CRS clinical IoR or designee or a primary HIV care provider. The HVTN 805/HPTN 093 PSRT should be consulted on possible ARS diagnosis. Participants with this diagnosis will re-initiate ART as soon as possible.

Signs and symptoms that may support a diagnosis of ARS include, but are not limited to, unintentional weight loss > 5% of pre-ATI body weight, otherwise unexplained persistent fever [$> 38^{\circ}\text{C}$], persistent night sweats, persistent diarrhea, oral candidiasis, and generalized lymphadenopathy.

7 Study products

There are no study products. Drugs for ART and PrEP will not be provided by the study or paid for using sponsor funds. Access to external funding sources for PrEP and ART provision is available. Procedures for accessing external funding sources for PrEP and ART provision are detailed in the HVTN 805/HPTN 093 SSP.

8 Laboratory

8.1 CRS laboratory procedures

The HVTN 805/HPTN 093 Site Lab Instructions and HVTN 805/HPTN 093 SSP provide further guidelines for operational issues concerning the clinical and processing laboratories. These documents include guidelines for general specimen collection, special considerations for phlebotomy, specimen labeling, whole blood processing, HIV screening/diagnostic testing, and general screening and safety testing.

Tube types for blood collection are specified in [Appendix E](#), [Appendix F](#), and [Appendix G](#). For tests performed locally, the local lab may assign appropriate tube types.

In specific situations, the blood collection tubes may be redirected to another laboratory or may require study-specific processing techniques. In these cases, laboratory special instructions will be posted on the protocol-specific section of the HVTN website.

Of note, all assays described below with the exception of HIV antiretroviral resistance testing are performed as research assays and are not approved for use in medical care. Results from these assays are not made available to participants or medical professionals to guide treatment decisions.

